10.5.2 Assessment of Homogeneity Across Stratification Variables

Heterogeneity across the randomization stratification variables of geographic region, genotype, and HCV/HIV co-infection status will be examined for the primary efficacy

endpoint of SVR₁₂ in Arm A using the chi-square test of homogeneity. The 14 strata are presented in Section 10.5.

If heterogeneity across the randomization stratification is detected, a confidence interval for the primary endpoint based on the 14 strata will be created using a stratum weighted variance calculated using the equations below. The variance of p_s will be estimated by:

$$Var(p_s) = \sum_{h=1}^H w_h^2 \frac{p_h(1-p_h)}{n_h - 1}$$

and the 2-sided 95% CI will be calculated as $p_s \pm z\sqrt{Var(p_s)}$, where z is the $1-\alpha/2$ point of the standard normal distribution. Note that n represents the number of subjects in Arm A within the ITT population, n_h represents the number of subjects in stratum h , w_h will be estimated by n_h/n , p_h = the proportion of subjects achieving SVR₁₂ in stratum h , and p_s = the proportion of subjects with SVR₁₂ among n subjects which can be defined as:

$$p_s = \sum_{h=1}^H w_h p_h$$

Using the equations above, a confidence interval for the SVR₁₂ rate across all 14 strata will be presented, along with the number and percentage (p_h) of subjects achieving SVR₁₂ within each of the 14 strata.

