## **8.0 Statistical Methods and Determination of Sample Size**

### **8.1 Statistical and Analytical Plans**

The primary analysis will occur after all subjects in Arm A have completed the PT Week 12 Visit or prematurely discontinued the study. The primary analysis will summarize data through PT Week 12 for Arm A subjects and data through the DB Treatment Period for Arm B subjects. The data for the primary analysis will be locked after data cleaning, and data collected after this lock will be added to a new version of the database. Results from the primary analysis will be described in the primary clinical study report (CSR) and submitted to regulatory agencies as part of an NDA submission. An interim analysis will occur after all Arm A subjects have completed the PT Week 24 Visit or prematurely discontinued the study and all Arm B subjects have completed the PT

Week 12 Visit or prematurely discontinued the study. The data for the interim analysis will be locked after data cleaning. Data collected after this lock will be added to a new version of the database which will be cleaned and locked at the end of the study.

SAS® (SAS Institute, Inc., Cary, NC) for the UNIX operating system will be used for all analyses. All statistical tests and confidence intervals will be two-sided with an alpha level of 0.05. Descriptive statistics will be provided, such as the number of observations (N), mean, and standard deviation (SD) for continuous variables and counts and percentages for categorical variables.

Analyses will be performed on the intent-to-treat (ITT) population defined as all randomized subjects who receive at least one dose of study drug in the DB Treatment Period, unless otherwise specified. The primary and secondary efficacy endpoints will be analyzed on the ITT population treated with active study drug in the DB Treatment Period (Arm A). Sensitivity analyses of the primary efficacy endpoint, when applicable, will be performed on the ITT population modified to exclude subjects of multiple GTs according to the central laboratory or phylogenetic analyses (mITT-GT), and on the mITT-GT population modified to exclude subjects who did not achieve SVR12 for reasons other than virologic failure (mITT-GT-VF). In addition, some analyses will be performed on the OL Population defined as all subjects who receive at least one dose of study drug during the OL Treatment Period.

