4.3 Sample Size

It is planned to enroll a total of approximately 504 subjects. In China, approximately 150 GT1-infected subjects will be randomized to receive active treatment (Arm A) or placebo (Arm B) in a 2:1 ratio; approximately 150 GT2-infected subjects will be randomized in a 2:1 ratio; and approximately 60 GT3, 4, 5, or 6-infected subjects will be randomized in a 2:1 ratio. Across Singapore and South Korea, approximately 105 GT1-infected subjects and approximately 39 GT2-infected subjects will be randomized to Arm A and Arm B; randomization will occur within each regional country in a 2:1 ratio. A maximum of 50 of the 504 subjects will have HCV/HIV co-infection across all countries. The expected approximate number of subjects by subpopulation is presented in [Table 1](#).

For the first primary endpoint, with a sample size of 336 GT1 – 6-infected subjects in the active treatment arm (Arm A) and assuming that 97% of these subjects will achieve SVR₁₂, this study has greater than 95% power to show non-inferiority to a historical control regimen, using a threshold of 90%, based on a 1-sample test for superiority using EAST 6.3. The threshold of 90% was based on a historical SVR₁₂ rate of 96% and a 6% non-inferiority margin (see Section 4.3.1). To establish efficacy, the lower bound of a 2-sided 95% confidence interval (CI) for the SVR₁₂ rate must be greater than 90% (based on a normal approximation of a single binomial proportion CI). No adjustment for dropouts is applicable because subjects who do not have data at PT Week 12 (after imputing) are counted as failures for SVR₁₂.

For the second primary endpoint, with a sample size of 170 GT1-infected subjects in the active treatment arm (Arm A) and assuming that 97% of these subjects will achieve SVR₁₂, this study has 90% power to show non-inferiority to a historical control regimen, using a threshold of 91%, based on a 1-sample test for superiority using EAST 6.3. The

threshold of 91% was based on a historical SVR₁₂ rate of 97% and a 6% non-inferiority margin (see Section 4.3.1). To establish efficacy, the lower bound of a 2-sided 95% CI for the SVR₁₂ rate must be greater than 91% (based on a normal approximation of a single binomial proportion CI). No adjustment for dropouts is applicable because subjects who do not have data at PT Week 12 (after imputing) are counted as failures for SVR₁₂.

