For the third primary endpoint, with a sample size of 126 GT2-infected subjects in the active treatment arm (Arm A) and assuming that 96% of these subjects will achieve SVR₁₂, this study has greater than 80% power to show non-inferiority to a historical control regimen, using a threshold of 89%, based on a 1-sample test for superiority using EAST 6.3. The threshold of 89% was based on a historical SVR₁₂ rate of 95% and a 6% non-inferiority margin (see Section 4.3.1). To establish efficacy, the lower bound of a 2-sided 95% CI for the SVR₁₂ rate must be greater than 89% (based on a normal approximation of a single binomial proportion CI). No adjustment for dropouts is applicable because subjects who do not have data at PT Week 12 (after imputing) are counted as failures for SVR₁₂.

Table 1. Summary of Approximate Subject Numbers Expected by Subpopulation

Sub-Population	DB Active	DB Placebo	Total
GT1	170	85	255
China	100	50	150
HCV/HIV Co-infected	10	5	15
Not HCV/HIV Co-infected	90	45	135
Asian Regional Countries	70	35	105
HCV/HIV Co-infected	6	3	9
Not HCV/HIV Co-infected	64	32	96
GT2	126	63	189
China	100	50	150
HCV/HIV Co-infected	10	5	15
Not HCV/HIV Co-infected	90	45	135
Asian Regional Countries	26	13	39
HCV/HIV Co-infected	2	1	3
Not HCV/HIV Co-infected	24	12	36
GT3 – 6	40	20	60
China	40	20	60
HCV/HIV Co-infected	4	2	6
Not HCV/HIV Co-infected	36	18	54
Total GT1 – 6	336	168	504
China	240	120	360
HCV/HIV Co-infected	24	12	36
Not HCV/HIV Co-infected	216	108	324
Asian Regional Countries	96	48	144
HCV/HIV Co-infected	8	4	12
Not HCV/HIV Co-infected	88	44	132

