12.0 Summary of Changes

12.1 Summary of Changes Between the Latest Version of the Protocol and SAP

1. Modified the definitions of the mITT populations to also exclude subjects who received incorrect duration of treatment due to incorrect classification of GT or treatment experience at randomization.
2. Removed the analyses of demographics, baseline characteristics, study drug exposure and compliance for the mITT populations because it is expected that these populations will be very similar to the ITT population.
3. Removed the analyses of demographics and baseline characteristics for the OL population because it is expected that this population will be very similar to the Arm B safety population.
4. Removed the analyses of study drug exposure and compliance for the GT1-infected and GT2-infected groups because these variables are expected to be similar between the set of all subjects and the GT1-infected and GT2-infected groups.
5. Replaced analyses by geographic region with analyses for the geographic region of China because analyses for the subset of subjects from China, rather than analyses by geographic region, are required by the regulatory agency. Certain analyses of subject disposition and SVR₁₂ will be performed by geographic region.
6. Added additional analyses of categorical baseline characteristics for subjects with HCV/HIV co-infection at Screening to provide additional information for the HCV/HIV co-infected population.

7. Added analyses of SVR₁₂ for Arm A for the geographic region of China to the sensitivity analysis to address regulatory requirements for China-specific analyses.
8. Added additional imputation approaches and assessment of homogeneity across stratification variables to the sensitivity analysis of the primary endpoints to align with the HCV ABT-493/ABT-530 program.
9. Removed the subgroup analysis of the primary endpoints for the mITT populations to align with the HCV ABT-493/ABT-530 program.
10. Added the additional efficacy analysis of the percentage of subjects with HCV virologic failure through PT Week 12 to align with the HCV ABT-493/ABT-530 program.
11. Removed several of the additional efficacy analyses to be performed on the HCV/HIV co-infected population because the number of HCV/HIV co-infected subjects is anticipated to be lower than had been expected at the time the protocol was written.
12. The PRO analysis as defined in the protocol:

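### SAP 10.5.2: the 14-stratum chi-square homogeneity test rejects about 10–15% of the time at a nominal 5%, and the stratified variance it triggers is undefined at the planned stratum sizes

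*SAP*

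**What the plan says.** SAP 10.5.2 belongs to the sensitivity analyses of SVR12. It tests homogeneity across region, genotype and HIV status in Arm A "using the chi-square test of homogeneity. The 14 strata are presented in Section 10.5". On a positive result, "a confidence interval for the primary endpoint based on the 14 strata will be created using a stratum weighted variance". With w_h = n_h/n, that variance is the sum over strata of w_h² p_h(1 − p_h)/(n_h − 1).

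Section 10.5.2 gives no significance level for the test, no exact or Monte Carlo alternative, no pooling rule, and no rule for a stratum with no subjects or one subject. The general rule in Protocol 8.1 is "All statistical tests and confidence intervals will be two-sided with an alpha level of 0.05". The only small-sample rule in SAP 10.5 withholds an interval when a summary has fewer than 10 subjects. The overall summary has about 336, so that rule reaches neither the test nor the individual variance terms.

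SAP Table 1 gives planned counts for China and for the regional countries together. The regional GT2 co-infected row (active, placebo, total) reads "HCV/HIV Co-infected 2 1 3". Section 10.5 divides those 2 Arm A subjects between a Singapore stratum and a South Korea stratum. SAP 12.1 adds that "the number of HCV/HIV co-infected subjects is anticipated to be lower than had been expected at the time the protocol was written".

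**The concern.** A Pearson chi-square needs reasonable expected counts in both outcome categories. Here the response rate is near 97%, and seven of the 14 strata hold co-infected subjects only, planned at 10 or fewer each in Arm A. A single failure in a very small stratum can carry the whole statistic, so the p-value may signal heterogeneity where none exists.

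The variance formula is weakest in those same strata. If the test is positive, the programmer may face terms that cannot be computed and would have to choose a convention after seeing the data. At stake are the credibility of a reported homogeneity p-value and the reproducibility of a supplementary interval.

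**Working it through.** **Inputs.** Arm A size: "with a sample size of 336 GT1 – 6-infected subjects in the active treatment arm (Arm A") (SAP 4.3). Rate: "assuming that 97% of these subjects will achieve" SVR12 (SAP 4.3), taken as common to all strata under the null. China strata from SAP Table 1: 10, 90, 10, 90, 4, 36. Regional totals: 6 and 64 (GT1 co-infected and not), 2 and 24 (GT2). Assumptions: the country split, which was varied, and the 0.05 level from Protocol 8.1.

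**Reproducing a stated figure.** The SAP gives no operating figure for the homogeneity test, so the inputs were checked against its power statement for GT1 (n = 170, 97% against 91%):

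Φ{[0.06 − 1.96·√(0.91·0.09/170)] / √(0.97·0.03/170)} = Φ{(0.06 − 0.0430)/0.0131} = Φ(1.30) = 90.3%, against a stated 90%.

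**Expected failures.** 336 × 0.03 = 10.1 in total. The largest stratum expects 90 × 0.03 = 2.7, so all 14 are below 5. With an even country split the smallest expects 0.03.

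**False-alarm rate.** Trials were simulated under a common rate. Empty strata were dropped and the degrees of freedom reduced. With 13 degrees of freedom the 5% critical value is 22.36. There were 200 country splits, with 40,000 trials each.

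| Common SVR12 | Range over splits | Median | Splits above 10% |
|---|---|---|---|
| 96% | 9.0–17.0% | 12.2% | 86% |
| 96.5% | 9.5–16.3% | 12.1% | 96% |
| 97% | 10.3–14.8% | 12.4% | all |
| 98% | 10.1–15.9% | 12.8% | all |

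The 96.5% row matches the unrounded Table 3 average: 0.51·97 + 0.37·96 + 0.07·97 + 0.05·95 = 96.5.

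**Mechanism.** One failure in a one-subject stratum adds about 0.97/0.03 = 32.3 to the statistic, which alone exceeds 22.36. With an even split there are two such strata. The chance of a failure in at least one is 1 − 0.97² = 5.9%, and 99.6% of those trials reject. Among the other trials 6.6% reject. Together: 0.059 × 0.996 + 0.941 × 0.066 = 12.1%. One-subject strata account for 48% of the false alarms in that case.

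**Is the reference distribution the cause?** The same 14-stratum statistic with an exact conditional critical value (even split) rejects in 5.1%, 5.1% and 4.9% of trials at 96%, 97% and 98%. The ordinary chi-square on five region-by-genotype groups (100, 100, 40, 70, 26) rejects in 4.7% at 97%.

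**Variance terms.** If n_h = 1, p_h is 0 or 1 and the term is 0/0. The 2 planned regional GT2 co-infected subjects split either 1/1 (two undefined terms) or 2/0 (one empty stratum, p_h undefined). If the plan is met, no split makes all 14 terms computable.

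**Effect on the interval.**
- Point estimate: p_s = Σ(n_h/n)(x_h/n_h) = x/n, where x_h is the number of responders in stratum h and x their total. This is the crude rate whatever the strata.
- For n_h ≥ 2, p_h(1 − p_h)/(n_h − 1) is unbiased for p(1 − p)/n_h. A one-subject term set to zero loses 1/336 = 0.3% of the total variance under a common rate.
- Simulated mean variance relative to the true value (200,000 trials per split): 0.994 (even), 1.000 (GT2 co-infected 2/0), 0.991 (3:1 with GT2 co-infected 1/1).
- Standard error relative to the crude one, in trials where the test rejects: 0.97, 0.995 and 0.96 for those splits. Over all trials: 0.997–1.001.
- At 97% the crude lower bound is 0.97 − 1.96·√(0.97·0.03/336) = 95.2%. After rejection the bound moves by 0.01–0.07 percentage points on average. In these 600,000 trials the stratified and crude bounds never disagreed about the 90% threshold.

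**The case against.** The strongest reply is that nothing important depends on this analysis. A reader might infer from "If heterogeneity across the randomization stratification is detected, a confidence interval for the primary endpoint based on the 14 strata will be created" that the stratified interval takes the place of the primary one. The documents do not support that. The primary interval and success rule are in SAP 10.3 and do not refer to this test, and 10.5 supplies normal-approximation and Wilson intervals whatever the test shows. The stratified interval is an addition. This part of the reply stands in full.

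A reader might also infer that strata with 100% response, which contribute no variance, make the interval too narrow. They do not when n_h ≥ 2, because the estimator is unbiased and larger terms elsewhere compensate. Only one-subject strata lose variance.

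Nor does every chance failure in a small stratum set off the test. At 97%, 62–69% of null trials have a failure in a stratum of 10 or fewer, and only 18–19% of those reject.

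The size of the inflation also rests on assumptions. The country split is not given and the 0.05 level is borrowed. At a 0.10 level the rate is about 15–17%, or 1.5–1.7 times nominal. If no co-infected subjects enrol, the size is about 5.8% at 97%; with only a handful it was 13–19%. So a flat statement that the rate is more than doubled would go too far.

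Finally, an empty stratum has zero weight and would naturally be dropped. That is a reasonable convention, but it is not written down, and it does not settle the one-subject case.

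**Conclusion.** The point holds as a defect in a sensitivity analysis. As written, the rule gives a p-value with the wrong size and calls for a variance that cannot be computed at planned enrolment.

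The false-alarm rate is about 10–15% at a nominal 5%, given SAP Table 1 counts, a common 97% rate and the protocol's general level; at 96% a few splits give about 9–10%. The undefined variance does not depend on which country split occurs if the 2 regional GT2 co-infected subjects enrol as planned. The lower co-infected enrolment expected in SAP 12.1 makes very small or empty strata more likely.

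The primary test and the point estimate are untouched. With undefined terms set to zero, the error in the supplementary standard error is small: about 0.5–4% too low on average after rejection, and negligible overall. The main harm is a misleading homogeneity p-value and a convention left to be chosen after the data are seen.

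**What to change.** In SAP 10.5.2:

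1. State the 0.05 level for the homogeneity test.
2. Replace the chi-square reference with an exact or Monte Carlo conditional p-value. This restores the size to about 5% with all 14 strata kept.
3. Pre-specify that strata with n_h ≤ 1 are pooled before the stratified variance is computed, for example into the region-by-genotype groups of SAP Table 1: China GT1, GT2 and GT3–6; regional GT1 and GT2. The smallest of these has 26 planned Arm A subjects, so every term is defined.
4. Keep the 14-stratum descriptive table as it is.

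The cost is a few sentences and a few lines of code, with slightly less country and HIV detail in the stratified interval. Sections 10.2 and 10.3 need no change.

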10.6 Efficacy Subgroup Analysis

Subgroup analyses will be performed for the primary efficacy endpoint of SVR₁₂.

Within each subgroup, the number and percentage of Arm A subjects achieving SVR₁₂ will be calculated for the set of all subjects in the ITT population and for each of the GT1-

infected and GT2-infected groups. The 2-sided 95% Wilson score CI will be produced if there are at least 10 subjects in the subgroup.

The following subgroups will be analyzed:

- HCV genotype and available subtype (based on the latest determination of genotype from the baseline sample [by the central laboratory or by phylogenetic analysis, with preference given to the phylogenetic analysis results] at the time of the primary SVR₁₂ analysis);
- Prior HCV treatment history (naïve or experienced);
- For treatment-experienced subjects, type of prior treatment experience (IFN- or SOF-based);
- For treatment-experienced subjects, type of non-response to previous treatment (on-treatment nonresponder or breakthrough, post-treatment relapse, or unknown/other);
- Screening HIV co-infection status (HCV mono-infected or HCV/HIV co-infected);
- IL28B genotype (CC or non-CC);
- Sex (male or female);
- Age (< 65 or ≥ 65 years) and (< 75 or ≥ 75 years);
- Geographic region (China, Singapore, or South Korea);
- Type of Asian descent (Chinese, Korean, Malay, or Other);
- Baseline BMI (< 30 or ≥ 30 kg/m²);
- Baseline HCV RNA level (< 1,000,000 or ≥ 1,000,000 IU/mL; < 6,000,000 or ≥ 6,000,000 IU/mL; < 10,000,000 or ≥ 10,000,000 IU/mL);
- Baseline HOMA-IR (< 2 or ≥ 2 mU × mmol/L²);
- Baseline fibrosis stage (equivalent to Metavir F0 – F1, F2, F3, F4 [if applicable]);
- Baseline platelet count (< 100 or ≥ 100 × 10⁹/L);
- Baseline albumin (< 35 or ≥ 35 g/L);
- Baseline creatinine clearance (< 60, ≥ 60 to < 90, or ≥ 90 mL/min);

- Baseline eGFR (C-MDRD) (< 60, ≥ 60 to < 90, or ≥ 90 mL/min/1.73 m²);
- History of diabetes (yes/no);
- History of bleeding disorders (yes/no);
- History of depression or bipolar disorder (yes/no);
- History of cardiovascular disease (yes/no);
- Baseline metabolic syndrome (yes/no);
- Injection drug use (yes, within last 12 months; yes, more than 12 months ago; or no);
- Baseline stable opiate substitution use (yes/no);
- Baseline hepato-protectant medication use (yes/no);
- Study drug compliance (yes/no);
- Concomitant use of PPIs (yes/no).

The summaries described above will also be performed for the geographic region of China within the overall set of Arm A subjects and the Arm A subjects in each of the GT1-infected and GT2-infected groups.

A logistic regression model will be used to explore the associations between each of the subgroup variables and SVR₁₂ by fitting a logistic regression model on all subjects in the mITT-GT-VF population. Among all candidate predictors, continuous measurements will be used where possible (e.g., continuous baseline log₁₀ HCV RNA level, continuous age, continuous BMI) in the logistic regression model. A stepwise logistic regression approach will be used to assess the strength of each subgroup variable in predicting SVR₁₂, with a significance level of 0.10 to enter and remain in the model.

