5.1.2 Modified Intention-to-Treat (mITT) Populations

Sensitivity analyses of SVR₁₂ as described in Section 10.5, when applicable, will be performed on the ITT population modified to exclude subjects who have multiple GTs according to the central laboratory or phylogenetic analyses of the baseline sample or subjects who received an incorrect duration of treatment due to incorrect classification of

GT or treatment experience at randomization (mITT-GT), and on the mITT-GT population modified to exclude subjects who did not achieve SVR₁₂ for reasons other than virologic failure (i.e., subjects with reasons other than on-treatment HCV virologic failure and relapse) (mITT-GT-VF).

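### The exploratory stepwise logistic model in SAP 10.6 offers 28 candidates to about 2.5 expected virologic failures, and does not say how two of them are coded for treatment-naive subjects

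*SAP*

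**What the plan says.** SAP 10.6 introduces its list with "The following subgroups will be analyzed" and gives 28 variables, from HCV genotype and subtype to use of proton pump inhibitors. Several take more than one degree of freedom. After the subgroup tables it adds a logistic model whose stated purpose is exploratory: it "will be used to explore the associations between each of the subgroup variables" and the response. The population follows: the model is obtained "by fitting a logistic regression model on all subjects in the mITT-GT-VF population". On selection the SAP says: "A stepwise logistic regression approach will be used to assess the strength of each subgroup variable in predicting" the response. The threshold is worded as "with a significance level of 0.10 to enter and remain in the model". For coding, it says only that "continuous measurements will be used where possible".

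SAP 5.1.2 defines mITT-GT-VF by removing, among others, subjects who missed SVR12 "for reasons other than virologic failure". SAP 10.1 restricts efficacy analyses to Arm A unless stated otherwise, so the model is read here as an Arm A model.

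Two list entries apply to part of the population only. One reads "For treatment-experienced subjects, type of prior treatment experience (IFN- or SOF-based"), and the next is the type of non-response to that earlier treatment. The SAP gives no value for treatment-naive subjects on either. It sets no minimum number of failures for fitting the model and no fallback if estimates do not exist. The ten-subject rule in 10.6 governs only whether a confidence interval is shown for a subgroup.

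**The concern.** A logistic model draws its information from the rarer outcome, here virologic failure. If a category contains no failure, or a combination of variables isolates the failures, the data are separated and maximum likelihood gives no finite odds ratio. With very few failures and a long list at 0.10, some variable will usually pass the entry test by chance.

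The two variables limited to treatment-experienced subjects add a second difficulty. A stepwise search compares candidates on a common set of records. How treatment-naive subjects are coded therefore decides who is in the model.

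At stake is whether this pre-specified look at predictors of failure can be interpreted. No primary or secondary result depends on it.

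**Working it through.** **The plan's own figure.** The SAP gives no event count for this model. The nearest planning figure is the expected overall SVR12 in SAP Table 3: 0.51×97 + 0.37×96 + 0.07×97 + 0.05×95 = 96.53%, which rounds to the stated 97%.

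**Ceiling on events.** Arm A has 336 subjects (SAP 4.3). At 97%, non-responders number 336 × 0.03 = 10.1; at the unrounded rate, 336 × 0.0347 = 11.7. These counts include non-virologic failures, which mITT-GT-VF removes.

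**Expected virologic failures.** Arm A has 170 GT1 and 126 GT2 subjects. Table 3 weights give GT3 0.07×336 = 23.5 and GT4–6 0.05×336 = 16.8. Failure counts come from Protocol Tables 5 and 7, non-cirrhotic subjects (on-treatment failures plus relapses, over subjects treated):

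| Group | Failures | Expected in Arm A |
|---|---|---|
| GT1, 8 weeks | 1/387 | 170 × 1/387 = 0.44 |
| GT2, 8 weeks | 2/197 | 126 × 2/197 = 1.28 |
| GT3, treatment-naive, 8 weeks | (1+5)/186 | 23.5 × 6/186 = 0.76 |
| GT4–6, 8 weeks | 0/58 | 0 |
| Total | | 2.48 |

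If all GT3 subjects instead failed at the 16-week treatment-experienced rate of 1/22, GT3 contributes 1.07 and the total is 2.79.

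As a cross-check, virologic failures were 3 of 12 non-responders in the non-GT3 8-week data, and 9 of 21 with treatment-naive GT3 added. Those shares of 10.1 give 2.5 to 4.3.

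**Spread around 2.48 (Poisson).**
- No failure: e^−2.48 = 0.084.
- At most one: 0.0837 × 3.48 = 0.29.
- At most five: 0.0837 × (1 + 2.48 + 3.075 + 2.542 + 1.576 + 0.782) = 0.96.
- At least five: 1 − 0.0837 × 10.673 = 0.11.

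**Events per candidate.** 2.5/28 = 0.09; at the ceiling, 10/28 = 0.36.

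**Chance entry.** For 28 independent null candidates, each tested at 0.10, the chance that at least one qualifies is 1 − 0.9^28 = 0.948.

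**Simulation.** Settings were 330 subjects, 26 independent candidates (the two treatment-experienced-only ones left out), no true association, assumed covariate prevalences, score-test entry at 0.10, and 150 runs per event count. Only entry was modelled; the removal step was not.

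| Failures | Separation reached on the stepwise path |
|---|---|
| 2 | 65% |
| 3 | 55% |
| 5 | 46% |
| 7 | 53% |
| 10 | 41% |

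At least one noise variable entered in 89% to 96% of runs. In every run at least one candidate separated the data on its own, and a model holding all candidates always separated.

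**The two restricted variables.** The documents give no treatment-experienced share for this trial. Protocol Table 6 has 139/387 = 36% in GT1 and 23/197 = 12% in GT2 at 8 weeks. At this trial's mix that is (170×0.359 + 126×0.117)/296 = 26%, taken here as an assumption. If treatment-naive subjects are missing on these variables, a complete-case fit keeps about 336 × 0.256 = 86 subjects (about 40 to 120 across 12% to 36%), and prior treatment history becomes constant. If they receive a not-applicable level, nobody is lost, but that level coincides with being treatment-naive and is collinear with prior treatment history.

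**The case against.** A reader might infer that the model is bound to separate, or that the plan excludes treatment-naive subjects. The documents support neither. Stepwise selection does not fit all 28 variables together, and separation on its path was common in the simulation but not universal. SAP 10.6 says all subjects, so a complete-case fit would contradict its own sentence. Protocol 8.1 limits imputation to SVR endpoints and questionnaires, which leans towards leaving values missing, but it does not settle the coding. The defect is an unstated rule.

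The 95% figure also needs care. The list is visibly correlated: creatinine clearance, eGFR and age; region and type of Asian descent; diabetes, HOMA-IR, BMI and metabolic syndrome. The effective number of candidates is below 28. The simulation also used independent candidates, so it does not remove this reservation.

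The analysis is labelled exploratory and lies outside the testing sequence of SAP 10.2. Nothing says that selected variables would be reported as established risk factors. Nor is this the only model of response: Protocol 8.1.6 plans exposure-response logistic regressions, and SAP 10.8 compares SVR12 by baseline polymorphism for South Korea and Singapore. Listings of non-responders or virologic failures are already planned in SAP 10.4, 10.7 and 10.8.

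All of this stands and limits the weight of the point. It does not show that the stated procedure can work with two or three events.

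**Conclusion.** The point holds as a weakness of an exploratory analysis. Following SAP 10.6 as written would probably give a model with no finite estimates, chance-selected predictors, or both. There is also about an 8% chance of no failures, in which case no model can be fitted. The coding gap is real under either reading: one drops the treatment-naive subjects, the other builds in collinearity.

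The size rests on three assumptions. Failure rates in this trial are taken to resemble the global 8-week data. GT3 subjects are given the treatment-naive rate. The separation frequencies depend on assumed covariate prevalences and on modelling entry only. The conclusion does not hinge on 2.5 exactly, since even the ceiling of 10 leaves 0.36 events per candidate. The primary and secondary endpoints and Type I error control are untouched.

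**What to change.** In SAP 10.6:
- Replace the stepwise selection with Firth-penalised or exact single-predictor logistic models, stated to be in Arm A of mITT-GT-VF.
- Use a short pre-specified list defined for every subject, for example genotype, prior treatment (yes/no), baseline log10 HCV RNA and fibrosis stage.
- Remove the two treatment-experienced-only variables from the model; they remain in the subgroup tables.
- Label the results descriptive.
- Pre-specify a minimum number of virologic failures, below which only the subgroup tables and the planned failure listings are given. The sponsor should choose it knowing that a minimum of five would be met only about one time in ten at 2.5 expected events.

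The cost is a wording change and simpler code. The multivariable screen of the minor covariates is lost, and the models may often not be run. The subgroup tables would still show SVR12 for every listed variable.
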